Subsequent studies using animal models of aging have reported that improvements in physical performance are greater in response to the combination of exercise and resveratrol than from either treatment alone.¹⁵⁻¹⁸ These studies overwhelmingly suggest that improvements in performance likely manifest as a result of enhanced skeletal muscle mitochondrial function. Thus, resveratrol appears to specifically target a key physiologic mechanism through which exercise improves physical function among older adults. We hypothesize that enhancing mitochondrial function may enhance physiologic adaptations to exercise such as aerobic fitness and skeletal muscle endurance. However, despite the promising findings from pre-clinical models, experimental data are sparse regarding the effects of this combined approach in humans. Consequently, well-controlled studies are needed to determine if the benefits of combining resveratrol with exercise demonstrated in pre-clinical studies can be translated to humans. *Therefore, the purpose here, as the next step in pursuit of our long-term goal, is to evaluate the relative efficacy of combining physical exercise with oral resveratrol supplementation for improving the physical function of older adults at risk for disability.*

5. Specific Aims:

The objective of this study is to conduct a pilot study to refine and finalize elements critical to conducting a future, definitive randomized, controlled trial (RCT). We propose to recruit 60 persons aged \geq 65 years with functional limitations and follow them for 12 weeks. Participants will be randomly assigned to receive either (1) placebo plus 2 days/week of supervised, center-based, multi-modal exercise (EX), or (2) the same exercise program combined with either 500 or 1000 mg/day of resveratrol (REX). We will also collect skeletal muscle biopsies at baseline and 12 weeks from willing participants (i.e. optional for study participation) to evaluate skeletal muscle mitochondrial adaptations to the interventions. This study will enable us to address the following aims, all of which are of critical importance for designing a full-scale trial.

1. To obtain critical data necessary to project the sample size needed for a full-scale trial using the change in 4m usual gait speed, a key predictor of health and survival in older adults,^{2,19,20} as the primary outcome.

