2. To determine the variance of secondary outcomes and short-term effects of the intervention on these outcomes, including: (1) exercise capacity, evaluated by distance walked during the 6-minute walk test, (2) lower-extremity function, assessed by the Short Physical Performance Battery (SPPB), (3) skeletal muscle strength and endurance, assessed by isokinetic muscle testing, and 4) self-assessed functional limitations, evaluated by the Late-Life Disability Questionnaire.
3. To (a) assess the effects of resveratrol on exercise-induced changes in key indices of skeletal muscle mitochondrial function and quantity, and (b) determine the extent of association between changes in these mitochondrial outcomes and changes in measures of physical function.

6. Research Plan:

We propose to conduct a randomized, controlled pilot trial to test that resveratrol improves functional responses of physically-limited older adults to chronic exercise training. Following study entry, participants (N = 60) will be randomly assigned to either EX or one of two REX groups for 12 weeks. Each condition will consist of two center-based resistance training sessions per week.

6.1 Participants: Eligible participants will be males or females ≥ 65 years of age with a sedentary lifestyle and objectively-measured functional limitations.

Table 6.1. Inclusion and exclusion criteria

Inclusion Criteria

• Age 65 years• > 290 seconds needed to complete long-distance corridor walk test, as an indicator of functional limitation and moderate to low aerobic fitness³• Sedentary lifestyle, defined as <150 min/wk of moderate physical activity as assessed by CHAMPS questionnaire²¹• Willingness to be randomized to either treatment group• Willingness to participate in all study procedures
Exclusion criteria

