
• Failure to provide informed consent;• Regular consumption of a resveratrol supplement• Current involvement in supervised rehabilitation program• Absolute contraindication(s) to exercise training according to American College of Sports Medicine guidelines²²• Pain classification $>$ Grade 3 on Graded Chronic Pain Scale²³• Peripheral vascular disease; peripheral neuropathy; retinopathy• Severe cardiac disease, including NYHA Class III or IV congestive heart failure, clinically significant aortic stenosis, history of cardiac arrest, use of a cardiac defibrillator, or uncontrolled angina;• Myocardial infarction or stroke within past year• Significant cognitive impairment, including known dementia diagnosis or a Mini-Mental State Examination exam score < 24• Progressive, degenerative neurologic disease, e.g., Parkinson's Disease, multiple sclerosis, ALS;• Severe rheumatologic or orthopedic diseases, e.g., awaiting joint replacement, active inflammatory disease;• Severe pulmonary disease, requiring either steroid pills or injections or the use of supplemental oxygen;• Hip fracture, hip or knee replacement, or spinal surgery within past 4 mos.;• Other significant co-morbid conditions that would impair ability to participate in the exercise-based intervention• Simultaneous participation in another intervention trial
FOR MUSCLE BIOPSY ONLY

• Use of prescription anti-platelet medications (not including aspirin)• Prescription anti-coagulant use (e.g. warfarin)• Conditions which reduce wound healing, e.g. peripheral vascular disease, venous stasis• Known allergy to lidocaine

6.2 Recruitment: Participant recruitment will be coordinated in conjunction with the *OAIC Clinical Research Core*, led by co-investigator [name]. We will develop a targeted recruitment approach based on previous experiences utilizing methods of recruitment that include direct mailings, newspaper classified and print ads, community luncheons and health fairs, as well as clinic referrals. We have been extremely successful in implementing this approach in past studies

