6.3 Screening and Study Entry: Interested individuals will initially complete a pre-screening interview by phone. Participants deemed eligible based on the pre-screening invited to an in-person screening visit. During this visit, potential participants will first be asked to give their informed consent and then will be screened for study entry criteria. Initial screening procedures will include a review of their medical history, physical activity habits, medication use, cognitive function (assessed by the Mini Mental State Exam), and a physical exam performed by a study physician. The study physician will review collected information relevant to potential participant's health and make recommendation on this individual's participation in this trial.

Participants will then be asked to complete the long-distance corridor walk test to evaluate functional status and aerobic fitness. If all study entry criteria are met, participants will be scheduled to return to the clinic for baseline assessments. In addition, the study participants will be asked to sign Medical Records Release Authorization. This Authorization will be used exclusively to obtain medical records to acquire facts, details, and outcomes of Serious Adverse Events that occurred during the study and have to be reported to the sponsor and/or IRB.

6.4 Baseline Assessment and Randomization: If all study entry criteria are met, participants will be scheduled to return to the clinic for baseline assessments prior to randomization. During this visit, participants will be asked to complete validated study questionnaires, including the Late-Life Disability Instrument²⁴ and provide a fasting blood sample for evaluation of clinical safety lab values. Participants will also complete the Short Physical Performance Battery (SPPB), a 6-minute walk test, and assessments of muscle strength. Finally, the study coordinator will provide participants with an armband physical activity monitor and dietary intake form to take home to objectively evaluate baseline physical activity and dietary habits. Staff members will then discuss randomization procedures with participants. Participants who agree to participate in the muscle biopsy procedure will be scheduled for a separate visit prior to initiation of study interventions.

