6.6 Adherence to interventions. To enhance adherence to the study interventions (compliance), we will utilize empirically-supported techniques which we have successfully utilized in prior studies. Our first step will be to fully inform participants of study requirements before randomization and enroll only those persons who are willing to complete all study procedures. Undoubtedly, however, issues arise after randomization with the potential to limit compliance. Common causes of poor compliance include vacations, spouse care, fatigue, and fluctuations in motivation, perceived lack of benefit, physical discomfort, and adverse health experiences. First, we have designed the trial, including the inclusion/exclusion criteria and physician monitoring, to limit the likelihood of experiencing adverse health events in response to the interventions. In addition, care will be taken by the interventionists to promote the safe engagement in the exercise intervention. For other issues of non-compliance, we will approach this potential problem using a social problem solving model ("toolbox") approach in dealing with individual adherence problems.²⁸ This approach assumes that the process of changing behavior is a collaborative effort between the participant and the interventionists, and that behavior change can be readily undertaken during the regular weekly contacts that intervention staff will initiate throughout the course of the intervention, as well as during face-to-face visits. Our team has successfully applied this type of problem-solving approach in promoting adherence to behavioral interventions in prior studies.

6.7 Follow-up and Close-out visits. In addition to baseline and screening visits, assessment visits will be conducted at 6 weeks (follow-up) and 12 weeks post-randomization. During the 6-week assessment visit, the research team will evaluate participant vital signs, collect blood samples, inquire about any adverse experiences since the last visit, and perform tests of physical performance evaluated performed at baseline. During the close-out (12 week) visit, the team will perform the same evaluations as during the 6-week visit, as well as administer study questionnaires, perform the SPPB, and collect home-based physical activity and dietary information from participants. Skeletal muscle biopsies will also be collected at 12 weeks from willing participants.

6.8. Primary and Secondary Outcome Measures.

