Measurement of skeletal muscle (1) *in situ* mitochondrial respiration, (2) proliferative activated receptor-γ coactivator 1α (PGC-1α), (3) mitochondrial DNA, (4) citrate synthase (CS) activity, and (5) cytochrome C oxidase (COX) activity will be completed the *OAIC Metabolism and Translational Science Core*, led by co-investigator [name]. Mitochondrial respiration will be determined immediately on freshly saponin-permeabilized muscle fibers as published previously⁸ using the high-resolution Oxygraph-2k (Oroboros, Innsbruck, Austria). Skeletal muscle PGC-1α, mitochondrial DNA content, as well as CS and COX activities will be determined using well-standardized, validated methods with excellent test re-test reliability in the Core laboratory.⁴²

6.10 Sample size justification. This study will help generate precise estimates of effect variance in the population in which a subsequent larger-scale study will be conducted. Published recommendations for the design of pilot studies indicate that a sample of 15-20 participants per randomized arm is typically sufficient to estimate a parameter for a future trial.⁴³⁻⁴⁵ The enrollment sample of 60 participants is intended to provide preliminary data necessary to indicate feasibility of a larger trial and to provide descriptive estimates of effects. It will also provide for nominal estimation (using a 95% CI) of mean changes in dependent variables within each arm. While it is possible that statistically significant differences between arms may be observed, this pilot trial is not intended to be powered to observe such differences with high probability. For aims 1 and 2, assuming $\alpha = 0.05$, we will have 80% power to detect an effect size of 0.74 for outcomes with three assessments (walking speed, muscle function, exercise capacity) and 0.79 for outcomes with two assessments (SPPB, self-assessed function, mitochondrial measurements), assuming a repeated measures correlation of 0.5. For the primary outcome of walking speed, we expect this detectable difference to be 0.12 m/sec based on a SD of 0.16 m/sec observed in the LIFE studies. For secondary aims, the following detectable effects sizes are expected based on our prior experience in LIFE and LIFE-P: SPPB, 1.3 points; 6-minute walk distance, 22.2 m; isokinetic peak torque, 27.8 Nm; and Late Life Disability Instrument Score; 3.8 points.

[figure not shown]

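### The 80% power at 0.79 SD claimed in section 6.10 for mitochondrial measurements assumes paired biopsies from essentially all 60 participants, yet the biopsy is optional

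*Combined protocol and SAP*

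**What the plan says.** Section 6.10 gives 80% power at an effect size of 0.74 for outcomes measured three times and "0.79 for outcomes with two assessments (SPPB, self-assessed function, mitochondrial measurements), assuming a repeated measures correlation of 0.5". Mitochondrial outcomes thus get the same figure as SPPB and self-assessed function, which are planned for everyone. The sentence is introduced as covering Aims 1 and 2, but the mitochondrial outcomes belong to Aim 3(a) in section 5, which is to "assess the effects of resveratrol on exercise-induced changes in key indices of skeletal muscle mitochondrial function and quantity".

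Those outcomes need muscle tissue at both time points, and the protocol treats the biopsy as voluntary:

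- Section 5 will "collect skeletal muscle biopsies at baseline and 12 weeks from willing participants (i.e. optional for study participation").
- Section 6.4: "Participants who agree to participate in the muscle biopsy procedure will be scheduled for a separate visit".
- Section 6.7: "Skeletal muscle biopsies will also be collected at 12 weeks from willing participants".
- Table 6.1 has exclusions for the biopsy alone, among them "Use of prescription anti-platelet medications (not including aspirin"), anticoagulants, conditions that impair wound healing, and lidocaine allergy.

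Two places point the other way. Table 6.1 lists as an inclusion criterion "Willingness to participate in all study procedures", and section 6.6 says to "enroll only those persons who are willing to complete all study procedures".

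The protocol gives no expected biopsy uptake, no size for the biopsy subsample and no allowance for missing pairs.

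**The concern.** A detectable effect calculated on the whole sample is attached to an outcome that only a voluntary, further restricted subsample can supply. A reader of section 6.10 would take the mitochondrial comparison to be as precise as one for which all participants are scheduled.

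The pilot is meant mainly for estimation, so precision is what matters. Section 6.10 cites 15 to 20 participants per arm as the usual size for a pilot. For Aim 3(a) that is met only if at least 15/20 = 75% of participants, 45 of 60, give paired samples. Nothing in the plan secures this.

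**Working it through.** **Inputs.** From section 6.10: alpha 0.05, power 80%, correlation r = 0.5, total 60, printed effect sizes 0.79 (two assessments) and 0.74 (three). From the abstract: three arms. Not stated and therefore assumed: a two-sided test, equal allocation (60/3 = 20 per arm) and a comparison of one arm with another. The effect sizes are in SD units, since 0.74 × 0.16 = 0.118, printed as 0.12 m/sec.

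**Reproducing the printed figures.** By the noncentral t with 2n − 2 degrees of freedom, 20 per arm detects 0.909 SD with 80% power on a single measurement. The variance factor for the mean of m assessments is (1 + (m − 1)r)/m.

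- m = 2: factor 0.75, and 0.909 × √0.75 = 0.787, printed as 0.79.
- m = 3: factor 0.667, and 0.909 × √0.667 = 0.742, printed as 0.74.

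The normal approximation, (1.960 + 0.842) × √(factor × 2/n), gives 0.787 and 0.742 at n = 19, and 0.767 and 0.723 at n = 20. The printed pair therefore implies 19 or 20 analysed per arm, that is 57 to 60 of 60.

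Other readings at N = 60 do not give both printed values:

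| Reading | Two assessments | Three assessments |
|---|---|---|
| One-sided test | 0.69 | 0.65 |
| Placebo v pooled resveratrol (20 v 40) | 0.68 | 0.64 |
| Alpha 0.025 | 0.87 | 0.82 |
| Three-arm F test, one arm differs | 0.76 | 0.71 |
| Three-arm F test, evenly spaced means | 0.87 | 0.82 |
| Pairwise, pooled 57 degrees of freedom | 0.78 | 0.74 |

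**Effect of fewer pairs.** Uptake is an assumption, so a range is shown. The columns are:

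- A: power at 0.79 SD, pairwise, factor 0.75.
- B: difference detectable with 80% power, pairwise, factor 0.75.
- C: the same for raw change, factor 2(1 − r) = 1.0.
- D: power at 0.79 SD for pooled resveratrol v placebo (n v 2n), factor 0.75.
- E: half-width of the within-arm 95% CI for mean raw change, t(0.975, n − 1)/√n, with SD of change 1.0 SD.

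| Pairs per arm (uptake) | A | B | C | D | E |
|---|---|---|---|---|---|
| 20 (100%) | 80.3% | 0.79 | 0.91 | 90.6% | 0.47 |
| 18 (90%) | 75.8% | 0.83 | 0.96 | 87.3% | 0.50 |
| 15 (75%) | 67.4% | 0.92 | 1.06 | 80.5% | 0.55 |
| 12 (60%) | 57.0% | 1.04 | 1.20 | 70.8% | 0.64 |
| 10 (50%) | 48.8% | 1.15 | 1.325 | 62.3% | 0.72 |

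At 19 pairs per arm (95%), A is 78.1% and B is 0.81.

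**The case against.** **The pilot disclaims power.** Section 6.10 says it is not designed to detect differences between arms with high probability. The sample size and the primary outcome do not rest on this phrase, and no mitochondrial effect is given in natural units. Since the sentence is headed for Aims 1 and 2, the phrase may have been carried along when outcomes were sorted by number of assessments. This stands and is why the point is minor. It does not correct a specific power figure attached to a named outcome.

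**All participants agree to all procedures.** The inclusion criterion and section 6.6 can be read that way. Section 5 expressly exempts the biopsy, section 6.4 treats agreement to it as a separate matter, and willingness cannot override a medical exclusion. How many the exclusions would remove is unknown. One example given for wound healing, peripheral vascular disease, is already a general exclusion.

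**The contrast is not stated.** Pooling the two resveratrol arms keeps 80.5% power at 15 v 30. That is true, but at full sample that contrast gives 0.68 and 0.64, so it is not what section 6.10 calculated. It falls to 71% at 12 v 24.

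**Other outcomes also lack a dropout allowance.** This is correct, and SPPB and gait speed likewise assume that all are analysed. An optional procedure adds a loss beyond ordinary attrition, but the fix below does not address the general gap.

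**The 0.75 factor is not tied to an analysis of change.** This is fair. As the variance of a mean of two assessments it includes baseline. It suits a baseline-adjusted comparison only because 1 − r² is also 0.75 at r = 0.5. For raw change, column C applies and the detectable differences are larger.

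**Conclusion.** The concern holds and is minor. The 0.79 is not miscalculated. It is a full-sample figure applied to an outcome for which the plan does not secure the full sample. On the pairwise reading that reproduces both printed values, it needs 95 to 100% paired biopsies. At an assumed uptake of 50 to 75%, power at 0.79 SD is about 49 to 67% and the detectable difference 1.15 to 0.92 SD.

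This rests on equal allocation, a two-sided pairwise test and the stated correlation of 0.5. A baseline-adjusted analysis with a correlation of 0.7 would need only 14 pairs per arm, but section 6.10 fixes 0.5. Actual uptake is unknown, so the documents show an unsupported assumption and not a demonstrated shortfall.

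**What to change.** In section 6.10, delete *mitochondrial measurements* from the 0.79 group and add for Aim 3(a):

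> Biopsies are optional, so fewer than 20 paired samples per arm may be available. For a pairwise comparison of two arms (two-sided alpha 0.05, correlation 0.5, same variance factor of 0.75 as the 0.79 figure), 18, 15, 12 or 10 paired biopsies per arm give a detectable difference with 80% power of 0.83, 0.92, 1.04 or 1.15 SD; the within-arm 95% CI half-width for mean raw change (SD of change equal to 1.0 SD) is 0.50, 0.55, 0.64 or 0.72 SD.

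If the intended analysis compares raw change between arms, the detectable differences should instead read 0.96, 1.06, 1.20 and 1.325 SD.

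The cost is a two-word deletion and two sentences, with a less favourable stated precision for Aim 3(a). Sample size, randomisation, visits, procedures and the status of every aim stay as they are. The insert does not cover the association in Aim 3(b).

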6.5 Exercise Intervention: After random assignment to either the EX or the REX groups, participants will engage in a two days a week, center based resistance exercise intervention for 12 weeks. Following a brief warm-up, participants will be instructed to walk for 30 minutes at a 5-6 on the CR10 scale with encouragement for 10 minutes to be vigorous (7-8 on CR10 scale). Sessions will also include 30 minutes of strength exercises for both lower- and upper-body followed by flexibility exercises and balance training to promote cool-down. Participants will be introduced to exercises in such a way that they begin with lighter intensity and gradually increase. The progressive nature of the intervention is designed to minimize discomfort and prevent injury. During the first week of the intervention, resistance exercises will be performed using lighter resistance where the focus will be on learning proper technique. Resistance training will be performed using standard isotonic resistance training equipment.

Participants in the REX groups will be randomly assigned to receive, in a double-blind fashion, either 500 or 1000 mg/day of encapsulated resveratrol or placebo. The company Reserveage Organics (Gainesville, FL) provided the resveratrol and placebo capsules for our previous study and will provide both the resveratrol and placebo capsules for the proposed study. Placebo capsules will be identical to those including resveratrol. Our 12-week resveratrol pilot study demonstrated that resveratrol supplementation at a dose of 1000 mg/day was safe and improved markers of metabolic function (i.e., blood glucose) in overweight, older adults. This dosage is also in line with

another recent pilot study by Crandall et al. (2012) which demonstrated safety and improvements in glucose metabolism and insulin sensitivity in older adults (mean age = 72 years) following 1000 mg/day of resveratrol.²⁵ The low dose has been previously shown to be sufficient for improving mitochondrial function³ and will allow for comparison with findings from the only human study of REX to our knowledge published to date.^{26,27}

Data from the exercise interventions will be collected and stored in the study database. Following each session, participants will be asked to provide a rating of perceived exertion (RPE) for the session according to the Borg CR10 scale. Additional data collected includes session attendance, 1 repetition maximum, and repetitions completed for each exercise per session.

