The study participant will be provided with detailed instructions (discussion and a leaflet) on how to take care of the incision site. Study staff will make follow-up phone calls in the days following the procedure to monitor healing and any potential adverse events.

Center-based assessments and interventions will be conducted and supervised by trained staff who will monitor potential adverse experiences and symptoms. All assessors and interventionists receive CPR training and training on management of acute events including syncope, chest pain, acute dyspnea, focal neurological symptoms and abnormal vital signs. Portable defibrillators are available at each intervention and assessment site and all study staff have on-call access to the study physician and contact numbers for emergency services are. Institutional and community EMS services will be activated if needed. As indicated previously, participants will be taught the importance and proper method of warming-up prior to and cooling-down following structured activity sessions. If at any point during an exercise session, participants develop chest pain, shortness of breath, or dizziness, they will be instructed to rest and to contact the center and their physicians if these symptoms persist or recur with further exercise.

Blood pressure and heart rate will be measured before and after the resistance training at each center based session in participants who had experienced any of the following during a previous exercise session: decrease in diastolic blood pressure ≥ 20 mm Hg during the activity, increase in systolic blood pressure to ≥ 250 mm Hg or in diastolic blood pressure ≥ 115 mm Hg during the activity, increase in heart rate $\geq 90\%$ of age predicted maximum, unusual or severe shortness of breath, chest pain or discomfort, palpitations, light headedness, dizziness or feeling about to faint, a session had to be discontinued because of other symptoms, excluding musculoskeletal symptoms (e.g., knees, ankles, hips), reported by the participant.

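### Section 6.11 schedules session blood pressure and heart rate only after an earlier trigger event, so its pressure and heart-rate triggers cannot pick up a symptom-free participant

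*Combined protocol and SAP*

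**What the plan says.** The session rule is in section 6.11: "Blood pressure and heart rate will be measured before and after the resistance training at each center based session", applied "in participants who had experienced any of the following during a previous exercise session: decrease in diastolic blood pressure" of at least 20 mm Hg, and so on through a list of events. Three further entries are measured values: systolic pressure reaching 250 mm Hg, diastolic pressure reaching 115 mm Hg, and heart rate reaching 90% of the age-predicted maximum. The pressure entries are tied to the exercise itself: "mm Hg during the activity, increase in systolic blood pressure to". The remaining entries are symptoms, "unusual or severe shortness of breath, chest pain or discomfort, palpitations, light headedness, dizziness or feeling about to faint", and a session stopped for other, non-musculoskeletal symptoms.

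Section 6.5 describes the session. Participants are "instructed to walk for 30 minutes at a 5-6 on the CR10 scale with encouragement for 10 minutes to be vigorous", and "Sessions will also include 30 minutes of strength exercises". The data it lists for each session are perceived exertion, attendance, one-repetition maximum and repetitions. Section 6.7 places vital signs at the 6-week and 12-week assessment visits. Elsewhere in section 6.11, staff supervise every session, watch for symptoms, and receive "training on management of acute events including syncope, chest pain, acute dyspnea, focal neurological symptoms and abnormal vital signs".

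**The concern.** A participant enters monitoring by having had one of the listed events. For the pressure and heart-rate events, knowing that the event occurred requires the very reading that monitoring would supply. A participant whose blood pressure or heart rate responds abnormally, but who feels well, therefore has no scheduled route into monitoring.

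Numeric thresholds add something to a symptom list mainly in such a participant. Section 7 names post-exercise hypotension and cardiovascular events as exercise risks, and a small risk of harmful pressure rises from strength work. The participants are sedentary, aged 65 or over, of moderate to low aerobic fitness, and encouraged to walk vigorously for part of each session.

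There is also a mismatch of timing. The pressure thresholds describe what happens during exercise, but the readings given to monitored participants are taken on either side of the resistance training.

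**Working it through.** No formula in the plan bears on this point, so the check sets the sections side by side and counts sessions.

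1. **Which triggers need a reading** (section 6.11).
   - Need a reading: diastolic fall, systolic rise, diastolic rise, heart rate. That is 4.
   - Do not need one: shortness of breath; chest pain or discomfort; palpitations; light-headedness, dizziness or near-faint taken together; stopped session. That is 5.
   - This gives 4 of 9, but the ratio depends on how entries are grouped. Treating the two pressure rises as one entry gives 3 of 8, or 3 of 9 if light-headedness is listed separately. Splitting the faintness terms gives 4 of 10 or 4 of 11. Under every count, all the pressure and heart-rate triggers depend on a reading.

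2. **Whether another scheduled reading could supply the value.** Section 6.5 lists no pressure or heart rate among the session data. The vital signs in section 6.7 belong to assessment visits. The rest of section 6.11 covers supervision, symptoms and emergency response. None schedules a session reading.

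3. **Session counts** (2 sessions a week for 12 weeks, 60 participants).
   - Sessions per participant: 2 × 12 = 24.
   - Session 1: no scheduled reading for any of the 60, since none has a previous session.
   - No symptom trigger and no stopped session: 0 of 24 sessions read.
   - Symptom trigger at session 1: 24 − 1 = 23 later sessions, 23 × 2 = 46 occasions on which pressure and heart rate are taken. Such a participant could then show one of the four values.

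4. **Timing of those two readings.** Section 6.5 describes the walk before the strength work but does not expressly fix the order. Assume the walk comes first.
   - If the resistance training means the strength block, the first reading falls after the walk and the second after the strength work. Nothing is scheduled before the walk, so a diastolic fall across the walk cannot be calculated.
   - If it means the whole session, as section 6 may suggest ("Each condition will consist of two center-based resistance training sessions per week"), the readings bracket everything. The closing one does follow the walk, but only after the strength block as well.
   - Under either meaning, no reading is scheduled during the walk.

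The documents give no rate of abnormal symptom-free responses, so the number missed cannot be estimated.

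**The case against.** The best case against is that little depends on this rule. The only stated consequence of meeting a trigger is more readings at later sessions. No stop, withdrawal or physician review is attached to the four values. The protections that act at once are the symptom-based rest and stop rules, and they apply from session 1. Table 6.1 excludes severe cardiac disease, recent myocardial infarction or stroke, and absolute contraindications to exercise. Section 6.3 adds a physician's examination. Section 6.11 adds constant supervision, on-call physician access and precautions when participants rise. All of this stands, and it limits the seriousness of the point.

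It also rules out some stronger readings that a reader might infer:

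- That the whole rule is circular. It is not: the symptom and stopped-session triggers need no reading and do start monitoring.
- That staff are barred from taking other readings. The plan does not say so. The word *only* is an inference from the absence of any other scheduled session reading. Staff are trained on abnormal vital signs and may take one. Section 6.11 also says procedures are adapted from earlier studies, whose operating detail may include routine readings.
- That participants exercise without protection, or that a stopping safeguard has been lost. The documents support neither.

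What the objection does not answer is that these protections respond to something seen, reported or found at screening. None schedules the reading that the four thresholds need.

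**Conclusion.** The point holds in limited form. Followed exactly, section 6.11 cannot use its own pressure and heart-rate thresholds to identify a participant who has had neither a symptom trigger nor a stopped session. This is a stated rule that does not work for that group, rather than a missing detail. The loss is the follow-up monitoring that the sponsor meant such a participant to have. The timing mismatch is a lesser defect: even in monitored participants, an extreme during exercise may pass unrecorded.

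The conclusion rests on the absence of any other session reading in the protocol. If a site manual already requires routine readings, one sentence saying so would close most of the gap. The change is worth making because it is cheap, it concerns safety, and the pilot is meant to settle procedures for a larger trial. Sample size, power and the gait speed analysis are unaffected.

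**What to change.** Replace the rule in section 6.11 with text to this effect:

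> *Blood pressure and heart rate are recorded for every participant before exercise, in the last minutes of the walk (or immediately after it), and after the strength block, at session 1, at one session after the 2-3 week build-up, and at one session near week 8. Anyone who meets a listed value or symptom has the same three readings at every later session.*

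Spreading the sessions matters because resistance is deliberately light at the start. The study physician should confirm that the pressure thresholds suit any reading taken just after exercise, since such a reading can miss a peak during it.

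**Cost.** 3 sessions × 3 readings × 60 participants = 540 readings. At an assumed 2 to 4 minutes each:
- 540 × 2 / 60 = 18 hours to 540 × 4 / 60 = 36 hours over the trial;
- 3 × 2 = 6 to 3 × 4 = 12 minutes per participant at each of the three sessions, by staff already supervising.

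A participant triggered at session 1 would have 23 × 3 = 69 later readings instead of the present 46. How many will trigger is unknown, so that part of the cost is not totalled.

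**Limit.** Readings for all cover 3 × 60 = 180 of 24 × 60 = 1,440 participant-sessions (12.5%). Other sessions remain under the trigger rule, but every participant would have scheduled chances to show a measured trigger, including at training intensity.
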